#### **11.1.3.2 Secondary endpoints/outcome measures**

[figure not shown]
- Change in the total LCSS score, ASBI score and individual domain scores from enrolment to each post-baseline predefined timepoints; in addition change throughout the study observation period will be examined using longitudinal analysis;
- Proportion of patients (n, %) with reported problems for each level for each dimension of EQ-5D and proportion of patients with 'no problems' (i.e., level 1) and 'with

[figure not shown]
*problems'* (i.e., level 2 & 3) at enrolment and at the post-baseline predefined timepoints;

- EQ-visual analogue scale (VAS) score (mean  $\pm$  SD) at enrolment and at the post-baseline predefined timepoints;
- Change in the proportion of patients in each of the EQ-5D dimension levels (no problems, with problems) and change in the EQ-VAS score between enrolment and post-baseline predefined timepoints;
- Change in ECOG PS scores from baseline to post-baseline predefined timepoints;
- Ratio of doses actually taken to doses prescribed over the study participation period and reasons for discrepancies;
- Proportions of patients with treatment discontinuations, temporary interruptions, or dose change(s) and reasons for treatment modifications.

## **11.3 STUDY TREATMENT**

### **11.3.1 Dosing/method of administration**

Each afatinib film-coated tablet contains 50, 40, 30 or 20 mg active substance (as afatinib dimaleate) and lactose (as monohydrate) as known active ingredient. For the full list of excipients please read the Summary of Product Characteristics.

When assessing a patient's EGFR mutation status, it is important that a well-validated and robust methodology is used to avoid false negative or false positive results.

According to the Summary of Product Characteristics, the recommended afatinib dose in first-line therapy is 40 mg once daily taken orally. Afatinib should be taken without food. Afatinib should be taken 3 hours after and at least 1 hour a meal. Afatinib is taken orally. The tablets are swallowed in one piece with a glass of water. For patients who are unable to swallow the afatinib tablets in one piece, they can be dissolved in about 100 mL of non-carbonated drinking water. Do not use any other liquids for this. The tablets are placed in one piece into the water without breaking them up beforehand. After that the contents of the glass is stirred occasionally for up to 15 minutes until the tablet has dissolved into very small particles. Drink the dispersed solution immediately, then rinse the glass with about 100 mL of water and also drink this water. The dispersed solution can also be administered via a gastric tube. A forgotten afatinib dose should be taken on the same day as soon as the patient remembers it. However, if the time until the next planned dose is less than 8 hours, the patient should not take the forgotten dose.

The treatment with afatinib should be continued until disease progression or until the patient no longer tolerates the medicinal product. A dose escalation to a maximum of 50 mg/day may be considered in patients tolerating the dose of 40 mg/day well in the first 3 weeks (i. e. absence of diarrhoea, rash, stomatitis and other drug-induced events of CTCAE grade >1). The dose should not be escalated in any patients with a prior dose reduction. The maximum daily dose is 50 mg.

### **11.3.2 Dose adjustment due to adverse events**

Symptomatic adverse reactions (e. g. severe/persistent diarrhea or skin-related adverse reactions) can usually be managed successfully by interrupting the treatment and reducing the dose or by discontinuing afatinib:

Adverse reactions according to CTC	Recommended afatinib dose:	
Grade 1 or Grade 2	No interruption 	No dose adjustment
Grade 2 (prolonged  or intolerable) or Grade >3	Interrupt until grade 0/1 	Resume with dose reduction in 10 mg decrements 

1. *NCI Common Terminology Criteria for Adverse Events*
2. *In case of diarrhoea, patients should take anti-diarrhoeal drugs immediately (e. g. loperamide) and continue to take these drugs in case of persistent diarrhoea until loose bowel movements abate.*
3. *>48 hours of diarrhoea and/or > 7 days of rash*
4. *If the patient cannot tolerate 20 mg/day, permanent discontinuation of the treatment with afatinib should be considered.*

### **11.3.3 Special warnings and precautions for use**

Diarrhoea, including severe diarrhoea, has been reported in patients treated with afatinib. Diarrhoea may result in dehydration (with or without renal impairment), which in rare cases has resulted in fatal outcomes. Diarrhoea usually occurred within the first two weeks of treatment; grade 3 diarrhoea most frequently occurred within the first six weeks of treatment. Proactive treatment of diarrhoea including adequate hydration combined with anti-diarrhoeal drugs especially within the first 6 weeks of the treatment is important and should start at first signs of diarrhoea. Anti-diarrhoeal drugs (e.g. loperamide) should be used and if necessary their dose should be escalated to the highest recommended approved dose. Anti-diarrhoeal drugs should be readily available to the patients so that treatment can be initiated at first signs of diarrhoea and continued until loose bowel movements cease for 12 hours. Patients with severe diarrhoea may require interruption of the treatment with afatinib, dose reduction or discontinuation of therapy. Dehydrated patients may require administration of intravenous electrolytes and fluids. Patients are therefore instructed to initiate treatment of diarrhoea with anti-diarrhoeal therapy independently and to inform the attending doctor of this immediately.

Rash/acne has been reported in patients treated with afatinib. In general, rash manifests as a mild or moderate erythematous and acneiform rash, which may occur or worsen in areas exposed to sunlight. Early treatment (such as emollients, antibiotics) of dermatic reactions increases the probability of treatment continuation. Patients with severe skin reactions may also require temporary interruption of therapy, dose reduction, additional therapeutic intervention, or referral to a specialist with expertise in managing these adverse dermatic reactions.

In the event of acute or aggravating respiratory symptoms, interstitial lung disease (ILD) must be considered and afatinib treatment should be interrupted until the cause of these symptoms has been clarified. If interstitial lung disease is confirmed, afatinib must be permanently discontinued and appropriate treatment initiated.

Afatinib is not recommended for use in patients with severe renal impairment (creatinine clearance < 30 mL/min) and hepatic impairment (Child-Pugh score C).

Higher plasma levels of afatinib have been observed in female patients, patients with lower body weight and those with underlying renal impairment. This could result in a higher risk of developing adverse reactions including diarrhoea, rash/acne and stomatitis. Closer monitoring is recommended in patients with these risk factors. For more information please read the respective Summary of Product Characteristics, in particular the sections on "Contraindications", "Warnings and precautions for use", "Interaction with other medicinal products and other forms of interaction" as well as "Fertility, pregnancy and breast-feeding".

Further information about afatinib can be found in the enclosed Summaries of Product Characteristics.

## **11.4       VARIABLES**

### **11.4.1      Primary outcome variable**

- ASBI score of LCSS -defined as the mean of the score of the 6 major lung cancer symptoms, i.e. loss of appetite, fatigue, cough, dyspnea, pain, and hemoptysis- at enrollment and at the 2-month intervals until the study visit at 6 months.

### **11.4.2      Secondary outcome variables**

- Patient-rated ASBI score of LCSS at the post-baseline predefined timepoints (these timepoints are defined in Section [11.1.2](#));
- Patient-rated total LCSS score -defined as the average of the aggregate score of all 9 items that comprise the LCSS- at enrollment and at the post-baseline predefined timepoints;
- Patient-rated individual LCSS domain scores at enrolment and at the post-baseline predefined timepoints;
- Proportion of patients with reported problems for each level for each dimension of EQ-5D and proportion of patients with 'no problems' (i.e., level 1) and 'with problems' (i.e., level 2 & 3) at enrolment and at the post-baseline predefined timepoints;
- EQ-VAS score at enrolment and at the post-baseline predefined timepoints;
- ECOG PS score at baseline and at the post-baseline predefined timepoints;

- Ratio of doses actually taken to doses prescribed over the study participation period and reasons for discrepancies;
- Proportions of patients with treatment discontinuations, temporary interruptions, or dose change(s) and reasons for treatment modifications.

#### **11.4.3 Other variables**

➤ ***Sociodemographic and anthropometric patient characteristics:***

- Age (years)
- Gender: *males, females (n, %); male-to-female ratio*
- Race: *Caucasian, Asian, African, other;*
- Place of residence: *urban areas, semi-urban areas, rural areas;*
- Educational level: *no education, primary education, secondary education, tertiary education;*
- Marital status: *single, married, divorced, widowed;*
- Employment status: *unemployed, employed, retired, household duties, other;*
- Smoking status: *never smoker, former smoker, occasional smoker, current smoker; if former or current smoker: smoking pack-years, and if former smoker: years since quitting smoking;*
- Weight (kg);
- Height (cm);
- Body mass index (BMI in kg/m^2);
- Systolic and diastolic arterial pressure (mmHg);
- Respiratory rate (bpm [breaths/minute]).

➤ ***Disease & clinical characteristics***

- Age at disease diagnosis;
- Disease stage (IIIB, IV) at baseline;
- Histologic classification (*adenocarcinoma squamous-cell-carcinoma, other*);
- EGFR mutation subtype (*exon 19 deletions, Leu858Arg, other*);
- Sites of metastases at baseline;
- Previous disease-related treatment patterns;
- Baseline comorbid conditions;
- Change in disease status throughout the study period.

➤ ***Treatment characteristics***

- Time from diagnosis to afatinib treatment onset;
- Length of exposure to afatinib treatment throughout study duration;
- Starting dosage regimen;
- Type of dose modifications over the study observation period;
- Concomitant medications both at baseline and throughout the conduct of the study.

#### **11.4.4 Confounding/effect modification variables**

The following variables will be considered as potential confounders or effect modifiers of the main association between treatment with afatinib and change in disease-specific symptom burden.

- Age at baseline;
- Gender;
- BMI at baseline;
- Educational/marital/employment status;
- Baseline comorbidity count with particular emphasis on gastrointestinal, psychiatric, and musculoskeletal and connective tissue disorders;
- Concomitant medications both at baseline and at the time of symptom burden assessment with particular emphasis among others on analgesics, antitussives, antidepressants, antiemetics, and antidiarrheals;
- Disease stage at baseline;
- Baseline ECOG PS;
- Baseline smoking status and lifetime tobacco exposure;
- Lung cancer histologic classification;
- EGFR mutation subtype;
- Sites of metastases at baseline;
- Adherence to afatinib treatment over the 6-month observation period and over the whole study participation duration.

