Population:	
A total of 128 patients are planned to be enrolled by seven (7) Oncology and Pulmonology hospital centres/clinics in Greece specialized in lung cancer. Physicians will originate from a random pool of specialists in lung cancer and will be recruited from various geographic regions in Greece in order for variations in clinical practice to be reflected. Investigators' selection will be performed by the means of a documented and constructed feasibility assessment process that will account, among others, for physicians' qualifications, previous participation and experience in similar clinical studies and recruitment potential and retention capability.
 
Patients who will be considered as eligible for participation in this study must meet ALL the following inclusion criteria and NONE of the exclusion criteria presented below:
 
Inclusion Criteria
 

• Adult outpatients (18 years and older) of either gender;

• Histologically or cytologically confirmed locally advanced or metastatic (IIIB/IV) NSCLC of any histological type with activating EGFR mutation(s) according to local laboratory EGFR testing;

• EGFR-TKI naïve patients;

• Patients for whom the decision to prescribe therapy with afatinib (GIOTRIF®) according to the locally approved product's summary of product characteristics (SmPC) has already been taken prior to

	
their enrolment in the study and is clearly separated from the physician's decision to include the patient in the current study;
 

• Patients must be able and willing to provide written informed consent and to comply with the requirements of this study protocol;

• Patients must have signed an informed consent document;

• Patients must be able to read, understand and complete the study specific questionnaires.

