## **10. RESEARCH QUESTION AND OBJECTIVES**

### **10.1 PRIMARY OBJECTIVE**

- To evaluate the impact of afatinib therapy on the patient-reported lung cancer-specific symptom burden, using the Average Symptom Burden Index (ASBI) of the LCSS in eligible patients, over 6 months of therapy, in a real world clinical setting in Greece.

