### **11.1.3 Study primary and secondary endpoints**

#### **11.1.3.1 Primary endpoint/outcome measure**

- 6-month symptom improvement rate using the LCSS ASBI, i.e., proportion of patients who will experience a minimum clinically important improvement in symptoms (*defined as a decrease in the ASBI from enrolment  $\geq$ 10 in two consecutive assessments*) over 6 months of treatment.

Note: A patient will be categorized as having:

- an **improved ASBI** if the mean of any two consecutive post-baseline ASBI assessments for that patient is at least 10 points below the patient's ASBI at enrolment;
- a **worsened ASBI** if the mean of any two consecutive post-baseline ASBI assessments for that patient is at least 10 points above the value at enrolment;
- a **stable ASBI** if the mean of any two consecutive post-baseline ASBI assessments for that patient is within 10 points of the value at enrolment.

[figure not shown]
A change of 10 points on a 0-100 scale is considered sufficient to indicate a clinically meaningful change [32, 33, 34]; this magnitude is about the same as the 0.5 standard deviation that has also reported as a universally acceptable minimum clinically important difference [35].

[figure not shown]

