### **11.8.2 Analysis for the primary endpoint**

Pertaining to the primary endpoint the proportion of patients experiencing a minimum clinically important symptom improvement (*as defined in Section 11.1.3.1*) over a 6-month period of treatment will be calculated along with the respective 95% confidence interval; in addition the relevant proportions of patients whose symptom burden has remained stable and deteriorated will be calculated. The 95% confidence interval will be derived from Wald confidence limits for a binomial proportion.

In order to examine the impact of baseline characteristics including among others, gender, age, BMI, educational/marital/employment status, disease stage, histological subtype, sites of metastases, EGFR mutation subtype, smoking status and smoking history, ECOG PS, type of concomitant medications and comorbidities, as well as adherence to therapy at 6 months on the study primary endpoint, a binary logistic regression model will be applied.

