## **11.10 LIMITATIONS OF THE RESEARCH METHODS**

The main foreseen limitations for this study are attributed to its observational design and mainly involve patient selection bias, information bias and missing data as well as lack of internal validity (no control group).

In order to control for and minimize patient selection bias, physicians will be requested to consecutively, thus non-selectively, enroll the first patients (based on the site-specific target) attending their clinic that meet the study specific eligibility criteria. In addition the investigators' decision-making to administer afatinib to a patient will be based on current medical practice and precede the consideration of the patient's eligibility for enrolment into the study. A screening log of all potentially eligible patients will be kept at site.

With regard to patient information/recall bias that may be introduced by the collection of data pertaining to patient-reported outcomes, this will be mitigated through the use of widely used PROs that employ no recall period as all questions refer to the symptoms and state of health at the day of completion. In addition, the self-administered PROs shall be completed by the patients themselves before the performance of any study-specific procedure(s) or clinical assessment(s) in order to avoid introducing any response bias.

In regards to the patient-reported symptom and HRQoL outcome measures, a potential confounding factor may arise from the fact that for patients for whom the onset of treatment with afatinib precedes their enrolment in the study, the completion of the PROs will not accurately reflect their baseline symptom burden and health state; nevertheless since the permitted time window between these two time points has been set at a maximum of 7 days, this time lag is not expected to significantly impact the robustness of the outcomes.

Another confounding factor to the patient-reported symptom and HRQoL outcomes is the potential effects of comorbidities and concomitant medications. To account for this, all baseline comorbid conditions as well as of concomitant medications both at baseline and throughout the conduct of the study (*with particular emphasis among others on analgesics, antitussives, antidepressants, antiemetics, and antidiarrheals*) will be collected in order to differentiate anticancer treatment effect from the effects of comorbidities and concomitant medication.

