The possible influence of confounding factors on the outcomes of this study will be accounted for in the statistical analyses by use of robust multivariable analyses, if deemed necessary.

With regard to the external validity i.e., the ability to generalize the study results to a more universal population, every effort will be made for the study population to be representative of the overall population of patients with NSCLC treated with afatinib in Greece by enrolling patients from geographically diverse locations throughout Greece with a non-limiting set of clinical characteristics, apart from those indicated by the locally approved product's SmPC, accounting for variations in medical practice paradigms.

Internal validity of the outcomes will be safeguarded to the extent feasible with the implementation of appropriate source data verification and quality assurance measures, as described in the relevant Section [11.9](#).

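### With every patient on afatinib and no control group, the promised adjustment for confounding of afatinib's effect cannot be made, and the raw improvement rate is not zero when nothing changes

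*Protocol*

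**What the plan says.** The primary objective is causal in wording: "To evaluate the impact of afatinib therapy on the patient-reported lung cancer-specific symptom burden" (Protocol 10.1). Enrolment is limited to patients already prescribed the drug; the inclusion criterion begins "Patients for whom the decision to prescribe therapy with afatinib" (Protocol Section 6).

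Three statements concern confounding:

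- Protocol 11.4.4 presents its covariates as "potential confounders or effect modifiers of the main association between treatment with afatinib and change in disease-specific symptom burden". The abstract and SAP 4.1 carry near-identical text.
- Protocol 11.10 says comorbidities and co-medication are collected "in order to differentiate anticancer treatment effect from the effects of comorbidities and concomitant medication".
- The same section says the influence of confounders "will be accounted for in the statistical analyses by use of robust multivariable analyses, if deemed necessary".

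The ENCePP checklist in Annex 2 answers yes on methods for confounding and for effect modification (items 10.5 and 10.6).

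The analysis specified in Protocol 11.8.2 is a raw proportion improved with a Wald interval, plus a binary logistic regression of that endpoint on patient characteristics and adherence. It adds that "the relevant proportions of patients whose symptom burden has remained stable and deteriorated will be calculated". On the 10-point threshold, Protocol 11.1.3.1 remarks that "this magnitude is about the same as the 0.5 standard deviation".

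**The concern.** A confounder or modifier of a treatment association needs a treatment contrast. Here treatment is constant, so the regression has no afatinib term. It estimates which treated patients improve, and leaves afatinib's effect neither estimated nor adjusted. Protocol 11.10 concedes the missing control group and then, within the same section, promises the separation that a control group would have been needed for.

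The second problem is the primary statistic. A proportion crossing a threshold in one direction is above zero even when nobody's underlying symptoms change, because scores vary from visit to visit. The protocol and the SAP text available set no reference rate against which to judge the observed one.

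Together, these could let an observed rate near the planning value of 0.50 be reported as afatinib's impact, with a statement that confounding was dealt with. The rationale (Protocol 9.3) says the results should help clinicians decide on treatment, so the wording matters.

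**Working it through.** **1. The plan's own figure.** Inputs from Protocol 11.6: p = 0.50, margin 0.10, 95% confidence, 25% non-evaluable.

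- n = 1.96² × 0.5 × 0.5 / 0.10² = 96.04, stated as 96.
- RSE = √(0.25/96) / 0.5 = 10.21%.
- 96 / (1 − 0.25) = 128.

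All reproduce. The interval of 0.40–0.60 describes the precision of a raw proportion. It does not separate a drug effect from fluctuation.

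**2. What the regression can estimate.** Exposure takes one value in the data set. Any coefficient in the 11.8.2 model therefore compares treated patients with other treated patients, for example by ECOG status or adherence.

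**3. The improvement rate with no true change.** Inputs:

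- Threshold of 10 points (Protocol 11.1.3.1).
- SD = 10 / 0.5 = 20, read from the half-SD remark. The documents state no ASBI SD.
- Scores at enrolment and months 2, 4 and 6 (Protocol 11.4.1), giving two consecutive pairs: (2,4) and (4,6).
- Normal scores with no mean change and equal correlation r between visits. The documents give no r, so it is assumed and varied.

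For one pair, the mean of two visits minus enrolment has variance SD² × 1.5 × (1 − r). At r = 0.5 this is 400 × 0.75 = 300, an SD of 17.3, and P(change ≤ −10) = Φ(−0.577) = 28%. At r = 0.8 it is 120, an SD of 10.95, and Φ(−0.913) = 18%. Because either pair may qualify, the patient-level rate is higher. Simulation of 2,000,000 patients per value of r gives:

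| r | Improved, mean of any pair | Worsened, same rule | Improved, fall of 10 at each of two visits |
|---|---|---|---|
| 0.5 | 36% | 36% | 22% |
| 0.6 | 33% | 33% | 20% |
| 0.7 | 30% | 30% | 18% |
| 0.8 | 24% | 24% | 14% |
| 0.9 | 14% | 14% | 7% |
| 0.95 | 5% | 5% | 2% |

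The last column is shown because 11.1.3.1 can be read both ways: its definition speaks of a decrease in two consecutive assessments, its Note of their mean.

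Sensitivity of the mean-of-pair rate:

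- Correlation that decays with time (AR(1)): 40% at r = 0.5 and 32% at r = 0.8.
- Scores clipped to 0–100 with an assumed underlying mean of 20 to 40: 31–35% at r = 0.5 and 20–24% at r = 0.8.

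**4. Improved minus worsened.** With no change and no selective loss, the expected difference is zero or close to it at every r above. Its 95% half-width is 1.96 × √[(pᵢ + p_w − (pᵢ − p_w)²)/n]. For illustrative values of 50% improved and 25% worsened at n = 96, this is 1.96 × √[(0.75 − 0.0625)/96] = 0.166, about ±17 points.

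**5. Overlapping categories.** Under the Note, one pair can be stable and the other not. In the simulation 24% (r = 0.8) to 31% (r = 0.5) of patients qualified as stable and also as improved or worsened. At most 0.4% qualified as both improved and worsened.

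**The case against.** The case against has several parts.

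- **The limitation is disclosed.** Protocol 11.10 names the absent control group, and 11.8 calls the analyses exploratory and descriptive. This stands: the fault is the claim of a remedy, not concealment.
- **Zero-centred measures are already planned.** Protocol 11.8.3 tests mean ASBI change from enrolment and, if applicable, fits mixed models, and 11.8.2 reports stable and deteriorated proportions. This stands too, so the improvement rate should not be described as the only evidence on change.
- **The headline is not adjusted.** A reader might infer that the improvement rate will be published as confounder-adjusted. The documents do not say so: 11.8.2 specifies a raw proportion, and describes the regression as examining the influence of patient characteristics on the endpoint.
- **The fluctuation figure is not the plan's own.** A reader might infer that 24–36% follows from equating 10 points with half an SD. It does not; it also needs an assumed correlation and the mean-of-pair rule.
- **Confounding is not meaningless here.** A reader might infer that nothing in this study can be confounded or modified. That goes too far: an adherence–response association can be confounded, and co-medication started during follow-up can be another cause of before–after change. Neither point gives the specified model an afatinib effect to adjust.
- **Net improvement is not immune to bias.** Observation ends at progression or death, and the PPS keeps only patients with endpoint data. With no true change, r = 0.7, and removal of patients who rise by 15 points or more at month 2 (an assumed rule, losing 17%), the simulation gives 35% improved against 19% worsened, a spurious difference of +16 points. This stands, so net improvement should be an added line and not the sole basis for conclusions.

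**Conclusion.** The concern holds in a limited form. The statements in Protocol 11.4.4 and 11.10 and SAP 4.1 promise control of confounding, or of effect modification, for an afatinib association that this design cannot estimate. That conclusion rests on the design alone and needs no numerical assumption.

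The size of the second problem is conditional. It assumes SD 20, normal scores and no true change. For equal correlation of 0.5 to 0.8, the improved share from fluctuation is 24–36% on the Note's rule and 14–22% on the each-visit rule. On the Note's rule it is about 14% at 0.9 and 5% at 0.95. About as many patients would be worsened in each case.

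These rates are benchmarks for no change. They should not be subtracted from an observed rate, and they do not show that any given share of a result near 0.50 would be noise. SAP Section 8, to which the SAP refers for the primary and adherence analyses, is not in the text available, and nothing here relies on its absence.

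**What to change.** 1. **Protocol 11.4.4, its abstract counterpart and SAP 4.1:** relabel the list as predictors of symptom improvement. Adherence and co-medication can stay on it in that role.
2. **Protocol 11.10:** delete the statements that confounding of afatinib's effect is accounted for, or that the treatment effect is differentiated from other causes. Bring the related checklist answers in Annex 2 into line.
3. **Protocol 11.8.2 and the matching SAP text:** beside the planned improved, stable and worsened proportions, report improved minus worsened with a 95% CI. State a rule that puts each patient in exactly one category.
4. **Interpretation:** read that difference together with the mean ASBI change in 11.8.3, and word conclusions as change observed during afatinib treatment. State that net improvement does not remove bias from selective dropout and does not establish causation.

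The cost is wording, one assignment rule and one extra line of output; no new data are needed. The downside is a less favourable headline and a wider interval for the difference: about ±17 points at n = 96 in the example above, against ±10 for the improvement rate, whose planned precision is unchanged.
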